9.8.2 Analytic Plan for the Secondary Objectives

Two-sample t test will be used to compare the mean change from baseline to 12 months for the secondary endpoints which hold the normality assumption. For endpoints that do not hold the normality assumption, as well as for ordinal level of measurements, Wilcoxon-rank-sum test will be used. To evaluate the changes in secondary endpoints across the different time points, repeated measures analysis of covariance will be used for continuous endpoints (appropriate transformation will be applied if normality assumption doesn't hold), while repeated measures generalized estimation equation with a cumulative logic categorical will be applied for the ordinal level of measurements. Generalized linear mixed models with adjustment for stratification factors and possible covariates will be applied to further characterize the patterns over the time and investigate the effect of the care type with appropriate link function. Results will be displayed in a graphical fashion. Patients who start medications known to affect endpoint being analyzed (e.g. statins for the lipid panel measurement) will be excluded from the main statistical analysis. In a sensitivity analysis these patients will be retained to assess impact of STAND clinic participation on study outcomes. No adjustment for multiple comparisons will be made for the analysis of the secondary, exploratory objectives.

For patients who cross-over from standard-of-care to participate in the STAND clinic, the mean change from month 12 to month 24 after twelve months of participation in the STAND clinic with respect to the study endpoints will be descriptively reported.

During the follow-up phase of the study, the mean change from completion of STAND clinic participation to 12 months after completion with respect to study endpoints will be descriptively reported.

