4.2 Exclusion Criteria

- Physically unable or unwilling to participate in recommended exercise programs or travel to UCSF on a monthly basis
- Presence of permanent pacemaker or implantable medical device.
 - Artificial joint prostheses and venous filters are allowed.

5. Study Drug

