9.7.2 Secondary Endpoints

Mean percent change from baseline to 12 months and patterns of change from baseline with respect to the following:

Metabolic Impact on Diabetes and Cardiovascular Disease Risk Factors:

- Fasting blood glucose
- Fasting plasma insulin level
- Insulin resistance as calculated by HOMA-IR
- Hemoglobin A1c
- Fasting lipids (total cholesterol, LDL, HDL, triglycerides)
- Waist circumference
- Body weight/body mass index
- Exercise patterns as measured by validated questionnaire and pedometer assessment
- Blood pressure

Bone Health:

- Bone density at the lumbar spine, femoral neck, and total hip as assessed by DXA scan among patients without bone metastases at the time of study entry
- Serum 25-(OH) vitamin D levels

Quality of Life/Psychosocial Impact:

- Depression as measured by PHQ-9
- Cognitive function as measured by Attentional Functional Index
- Overall quality of life as measured by SF-12
- Fatigue as measured by the Lee Fatigue Scale
- Erectile and urinary function as measured by EPIC-26
- Hot flash severity as measured by Hot Flash Related Daily Interference Scale

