Appendix 3. Charlson Co-Morbidity Index

Table 1. Charlson Comorbidity Index Scoring System

Score	Condition
1	Myocardial infarction (history, not ECG changes only) Congestive heart failure Peripheral vascular disease (includes aortic aneurysm ≥ 6 cm) Cerebrovascular disease: CVA with mild or no residua or TIA Dementia Chronic pulmonary disease Connective tissue disease Peptic ulcer disease Mild liver disease (without portal hypertension, includes chronic hepatitis) Diabetes without end-organ damage (excludes diet-controlled alone)
2	Hemiplegia Moderate or severe renal disease Diabetes with end-organ damage (retinopathy, neuropathy, nephropathy, or brittle diabetes) Tumor without metastases (exclude if >5 y from diagnosis) Leukemia (acute or chronic) Lymphoma
3	Moderate or severe liver disease
6	Metastatic solid tumor AIDS (not just HIV positive)

NOTE. For each decade > 40 years of age, a score of 1 is added to the above score.

Abbreviations: ECG, electrocardiogram; CVA, cerebrovascular accident; TIA, transient ischemic attack; AIDS, acquired immunodeficiency syndrome; HIV, human immunodeficiency virus.

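### Any man already using insulin at entry would stay in the fasting insulin and HOMA-IR analyses, because Section 9.8.2 excludes only men who start a drug

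*Combined protocol and SAP*

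**What the plan says.** - **Endpoints.** Section 9.7.2 lists "Fasting plasma insulin level" and "Insulin resistance as calculated by HOMA-IR" among the metabolic secondary endpoints, to be summarised as mean percent change from baseline to 12 months. The hypothesis in Section 2.1 refers to markers of insulin resistance and to fasting insulin and glucose.
- **Eligibility.** Section 4.1 is silent on diabetes and insulin. Section 4.2 has two exclusions: "Physically unable or unwilling to participate in recommended exercise programs or travel to UCSF on a monthly basis", and a pacemaker or other implanted device.
- **Baseline data.** Section 9.6 includes diabetes among the comorbidities to be described at baseline. Concomitant medications are recorded at screening and on Day 1 (Sections 7.1, 7.2 and 7.4.1).
- **Medication rule for secondary endpoints (9.8.2).** "Patients who start medications known to affect endpoint being analyzed (e.g. statins for the lipid panel measurement) will be excluded" from the main analysis. The accompanying sensitivity analysis only restores those men: "In a sensitivity analysis these patients will be retained to assess impact of STAND clinic participation on study outcomes".
- **Adjustment (9.8.2).** "Generalized linear mixed models with adjustment for stratification factors and possible covariates will be applied". The covariates are not named.
- **SNP analysis (9.8.3).** Change in fasting insulin is one of the responses. The section contains no medication exclusion.

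**The concern.** The plan accepts that a drug acting on an endpoint should keep a man out of that endpoint's main analysis, but applies this only to drugs begun on study. For fasting insulin the more troublesome case is the man who was injecting before Day 1. Both his baseline and his month 12 values then depend on the dose and on when it was given. HOMA-IR is calculated from fasting insulin and fasting glucose, so it inherits the problem.

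At stake is what these two endpoints mean. They are the plan's direct markers of insulin resistance, and both are reported as a mean percent change, a summary that a few extreme ratios can dominate.

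**Working it through.** **1. Follow the rules for two hypothetical men.**

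| | Starts insulin in month 2 | On insulin since before Day 1 |
|---|---|---|
| Eligible (4.1, 4.2) | yes | yes |
| 9.8.2 main analysis | out | in |
| 9.8.2 sensitivity analysis | in | in |
| 9.8.3 fasting insulin response | in | in |

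No planned analysis, main or sensitivity, sets the second man aside. Section 9.8.1 names insulin, but only when begun on study and only for body fat. Diabetes and insulin use are not stratification factors (7.3).

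**2. The plan's own figure.** Section 9.2 gives 32 evaluable men per arm for effect size 0.71, 80% power and two-sided 0.05. The normal approximation gives n = 2(1.96 + 0.84)² / 0.71² = 31.1, rounded up to 32. The noncentral t gives power 0.798 at 32. Enrolment is 32 / 0.80 = 40 per arm. These reproduce, but they concern body fat. The documents give no such figure for insulin or HOMA-IR, so 32 and 0.71 are only stand-ins below.

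**3. How many men?** The prevalence q of insulin use at entry is assumed. Expected users among 80 are 80q; the chance of at least one is 1 − (1 − q)^80; imbalance comes from two independent binomials with 40 men each.

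| Assumed q | Expected users | P(at least one) | P(arms differ by 2 or more) |
|---|---|---|---|
| 2% | 1.6 | 80% | 21% |
| 5% | 4 | 98% | 43% |
| 10% | 8 | above 99.9% | 57% |

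**4. Effect on a t test (illustration).** Assume users show no treatment effect and have a change SD k times that of other men. The effective effect size is 0.71(1 − q) / √[(1 − q) + qk²]. For q = 5% and k = 4 this is 0.6745 / 1.323 = 0.51.

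| Assumed q | Power, k = 2 | Power, k = 4 |
|---|---|---|
| none | 0.80 | 0.80 |
| 2% | 0.76 | 0.67 |
| 5% | 0.70 | 0.52 |
| 10% | 0.60 | 0.36 |

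**5. Effect on the rank test that 9.8.2 uses when normality fails.** In a simulation with 32 per arm, effect 0.71, users randomly placed with no effect and k = 20, power was about 0.78 with no users, 0.74 with one in total, 0.69 with three and 0.61 with six. The t test fell to 0.38 with one user. With a single extreme value placed adversely in the STAND arm, rank-test power was about 0.67.

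**6. Effect on the reported mean.** Take a deliberately extreme man whose measured insulin goes from 10 to 80 units, or +700%. He moves his arm's mean percent change by 700 / 32 = 21.9 points. On the absolute scale the shift is 70 / 32 = 2.2 units.

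**The case against.** The case against giving this much weight is strong, and most of it stands.

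- **No such man is documented.** The documents do not say that anyone on insulin was or will be enrolled. Appendix 3 does score "Diabetes with end-organ damage (retinopathy, neuropathy, nephropathy, or brittle diabetes"), but it is a generic comorbidity table and does not mention insulin treatment. The better support is Section 9.6, and it too shows only that diabetes is expected. The point is conditional on enrolment.
- **Bias.** A reader might infer that the arm comparison is biased. The documents do not support that. Insulin use at entry precedes randomisation, so it is balanced in expectation. Doses might change differently in the two arms, and a dose change is not a start, but the documents give no basis for saying that this happens or in which direction.
- **Outliers.** A reader might take the 22-point shift as the effect on the test. It is not: Section 9.8.2 provides a Wilcoxon test, or a transformation in the longitudinal models, when normality fails, and step 5 shows that the rank test loses far less than the t test. These provisions do not protect the reported mean, and they do not turn the values into a measure of insulin resistance.
- **Importance.** These endpoints sit in a long unranked list, and 9.8.2 makes no multiplicity adjustment. The documents do not designate them as key endpoints, and this point does not touch the primary endpoint.
- **Other glucose-lowering drugs.** One may ask why only insulin is singled out. The reason is measurement: with other drugs the assay still reads the man's own insulin, and with injected insulin it may not. That is a reviewer's judgement, not something the plan states.

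**Conclusion.** The gap is real and small. As written, the rules would keep a man who already injects insulin in the main and sensitivity analyses of fasting insulin and HOMA-IR, where his values do not measure his insulin resistance. The consequences are added variance, chance imbalance, a distorted reported mean percent change and lost interpretability, in secondary endpoints that carry no multiplicity control.

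The size cannot be settled from the documents. The tables rest on an assumed prevalence of 2% to 10%, assumed SD ratios, and body-fat design figures borrowed for another endpoint. They show that even a few users could matter, not that they will.

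Section 9.8.3 differs: its problem is not a rule limited to starters but the absence of any medication rule, so both baseline users and starters remain in its fasting insulin response.

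**What to change.** In Section 9.8.2 add: 'Fasting insulin and HOMA-IR are analysed in men not using insulin at Day 1; an analysis of all men is a sensitivity analysis.' The restriction uses a fact fixed before the intervention begins and already recorded, so the randomised comparison stays valid and no new data are needed.

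In Section 9.8.3, for the fasting insulin response only, apply the same Day 1 restriction and also the 9.8.2 exclusion for men who start insulin on study, again with an all-men sensitivity analysis. The exclusion of starters depends on events after baseline, which is a reason to report the all-men result beside it.

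The cost is a sentence in each section. The downside is that these endpoints lose the few men who use insulin at entry. Eligibility and treatment are unchanged.

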9.8.3 Analytic Plan for the Correlative Objectives

The relationship between each pre-selected SNP genotype and the percent change from baseline to 12 months on-study in percentage body fat, fasting plasma glucose, body mass index, waist circumference, and fasting insulin among men undergoing ADT will each be tested using a two-sample t test or Wilcoxon-rank-sum test as appropriate when the SNPs are in dominant or recessive fashion. When SNPs are in the additive model, for each SNP, a generalized linear model with an appropriate link will be used considering each baseline-12 month change as the response variable and SNP genotype (coded as 0, 1, and 2 for zero, one and two copies of minor allele) as the predictor. Analysis will be extended to adjust for possible risk factors by fitting multivariate generalized linear models for each baseline-12 month change and each SNP. Multiple testing adjustments will be done for each baseline-12 month change across all SNPs by controlling for false discovery rate.

The mean percent change from baseline in trabecular bone microarchitecture parameters including trabecular bone number and trabecular bone volume assessed by high resolution quantitative peripheral CT will be descriptively reported for the entire study population. In an exploratory fashion, the mean percent change between those randomized to the STAND versus usual care treatment arms will be compared using Mann-Whitney test.

The distribution of the 2D:4D finger length ratio will be determined for the entire study population. As the optimal cut-off to define sensitivity to androgen deprivation therapy is not known, the study cohort will be dichotomized into those with 2D:4D ratios above and below the median respectively. The mean percent change from baseline in QOL scores from the collected questionnaires as well as the baseline and mean percent change from baseline in empathy score will be compared between dichotomized subgroups using the Mann-Whitney test.

No adjustment for multiple comparisons will be made for the analysis of the correlative study endpoints.

10. Study Management

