	
different disciplines, clinics and services.
 
During the course of an integrated visit, the patient will have the following personalized assessment and counseling:
 
 • Patient care and counseling by a trained nurse practitioner and/or physician • Twelve monthly educational “modules” regarding ADT side effect management • Medication management including LHRH analogue injections during visit • Cardiovascular monitoring and risk reduction, including hypertension, hyperlipidemia, glucose monitoring, and cardiac risk stratification • Bone health monitoring and management • Nutrition counseling • Exercise training • Evaluation and counseling for relationship and mood changes by trained social worker • Assessment of quality of life and side effects of ADT with validated questionnaires (patients will also have opportunity to fill out questionnaires on-line ahead of clinic visit) 
The current randomized phase 2 cross-over study is designed to preliminary evaluate the longitudinal impact of participation in the “STAND” clinic (as compared to usual standard of care) on key metabolic parameters, quality of life, and patient satisfaction for men receiving hormone therapy for prostate cancer. Standard-of-care therapy will consist of every 3-month visits comprised of review of medical history, toxicity assessment, and lifestyle modification counseling provided by individual health care provider, LHRH analog injections by trained oncology nurse. Patients will have access to exercise, nutrition, and social work counseling if requested by patient or deemed necessary after consultation with health care provider. After 12 months on study, patients randomized to the usual standard-of-care arm will have the opportunity to cross-over and participate in the STAND clinic for the ensuing 12 months or for the remainder of ADT duration, whichever is shorter. Should the results indicate a beneficial impact of participation in a multi-disciplinary clinic in mitigating the short- and intermediate-term toxicities of ADT, this would form the justification for larger randomized clinical trials to assess the impact of clinic participation on longer-term co-morbidities including the incidence of diabetes, cardiovascular morbidity and mortality, and overall incidence of non-prostate cancer specific mortality.

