7.8 Concomitant Medications

Concomitant medications will be recorded at each study visit. The addition of medications to manage fasting blood glucose, lipids, bone density, or blood pressure will be allowed and at the discretion of the individual treating physician.

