9.2 Determination of Sample Size and Study Power

The sample size estimate is based upon the primary endpoint of the study, the mean percent change in percentage body fat from baseline to 12 months. Based on prior prospective longitudinal studies, it is estimated that men receiving ADT and standard-of-care physician counseling regarding expected toxicities will experience a mean 12% (sd = 17%) increase in percentage body fat after 12 months of ADT [13]. If men participating in the STAND clinic, with individualized exercise/nutrition counseling and longitudinal assessment, have, on average, no increase in percentage body fat mass after 12 months of hormone therapy, this would warrant further evaluation of a multi-disciplinary clinic in a larger randomized clinical trial with long-term endpoints of interest, including incidence of diabetes and potentially cardiovascular disease. An enrollment target of 32 evaluable patients per arm will provide power of 80% to detect an effect size of 0.71 in the difference in mean percent change from baseline to 12 months in percentage body fat mass between the two arms, using a two-sample t test and a two-tailed level of significance = 0.05. The total planned accrual is 40 patients per arm accounting for an inevaluable rate of 20%.

A sample size of 20 patients is chosen for the non-randomized chemohormonal cohort to establish the feasibility of a multi-disciplinary clinic in this patient population. The primary endpoint for this pilot cohort is the percentage of completed STAND clinic visits, with a target goal of 80%. A sample size of 20 patients (13 visits per patient; 260 visits in total) provides 17.5% precision to determine the percentage of completed visits at 95% confidence.

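### Section 9.8.3 tests SNPs and 2D:4D ratio on the pooled arms without using arm, which costs some precision but does not bias the tests

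*Combined protocol and SAP*

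**What the plan says.** Section 9.8.3 covers three sets of correlative analyses.

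- **SNPs.** The plan tests "The relationship between each pre-selected SNP genotype and the percent change from baseline to 12 months on-study in percentage body fat", together with the changes in fasting glucose, body mass index, waist circumference and fasting insulin. Dominant or recessive coding leads to a two-sample t test or Wilcoxon test; additive coding leads to a generalised linear model with genotype as the predictor. An extension adjusts for risk factors that are not listed.
- **2D:4D ratio.** The cohort is split at the median. Percent change in the quality-of-life scores, and baseline and change in empathy score, are compared between halves by Mann-Whitney test. No adjusted version is planned.
- **HR-pQCT.** Percent change in the trabecular parameters "will be descriptively reported for the entire study population". An exploratory Mann-Whitney comparison of STAND with usual care follows.

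On drugs, Section 7.8 states: "The addition of medications to manage fasting blood glucose, lipids, bone density, or blood pressure will be allowed". Section 9.8.1 removes men who start drugs affecting body fat from the primary analysis. Section 9.8.2 removes men who start drugs affecting a secondary endpoint from its main analysis and brings them back in a sensitivity analysis. Section 9.8.3 has no such rule and does not refer back to either.

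**The concern.** The SNP and 2D:4D questions ask whether a fixed trait predicts how a man responds to ADT. Half of the randomised men receive an intervention that Section 2.1 expects to reduce body fat gain, insulin and glucose changes, weight gain and quality-of-life decline. These largely overlap the response variables in Section 9.8.3. If STAND works, the difference between arms enters the SNP and 2D:4D tests as unexplained variance. Arm is known for every randomised man, so that variance can be removed at almost no cost.

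HR-pQCT raises a related question of description. The STAND programme in Section 1.1 includes "Bone health monitoring and management", so a single pooled mean averages two kinds of care. HR-pQCT is neither a primary nor a secondary endpoint, so no drug-starter rule clearly covers it.

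**Working it through.** **Inputs (Section 9.2).** Usual care: men "will experience a mean 12% (sd = 17%) increase in percentage body fat after 12 months of ADT". STAND: men "have, on average, no increase in percentage body fat mass after 12 months of hormone therapy". The arm difference is therefore 12 and the SD 17. Allocation is 1:1 (Section 7.3).

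**The plan's own figure.** "An enrollment target of 32 evaluable patients per arm will provide power of 80% to detect an effect size of 0.71", "using a two-sample t test and a two-tailed level of significance = 0.05".

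- Normal approximation: n per arm = 2 × (1.96 + 0.842)² / 0.71² = 15.70 / 0.504 = 31.1, rounded up to 32. With 12/17 = 0.706 it is 31.5, again 32.
- Exact t test: n = 32.1 (effect 0.71) or 32.5 (effect 0.706). Power at 32 per arm is 79.8% or 79.4%.
- Accrual: 32 / 0.80 = 40 per arm.

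The stated sample size reproduces. The documents give no power for the correlative analyses.

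**SD when arm is left out.** With 1:1 allocation and arm difference d, the variance is 17² + (d/2)².

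| Arm difference d | Variance | SD | Rise in SD | Information in 64 men |
|---|---|---|---|---|
| 12 (Section 9.2) | 289 + 36 = 325 | 18.03 | 6.0% | 64 × 289/325 = 56.9 |
| 6 (assumed) | 289 + 9 = 298 | 17.26 | 1.5% | 62.1 |
| 3 (assumed) | 289 + 2.25 = 291.25 | 17.07 | 0.4% | 63.5 |

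At d = 12 the variance ratio is 325/289 = 1.125.

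**Effect on power at d = 12.** Take 64 men split evenly by marker (assumption).

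- With SD 17, the marker difference detectable with 80% power is 12.1 points. With SD 18.03 it is 12.8 points.
- Power for the 12.1-point difference falls from 80% to 75.2%. The same 75.2% results for uneven splits (minor allele frequencies from 0.05 to 0.4, dominant coding).
- Simulation (20,000 runs) gives 79.2% with arm in the model and 75.3% for the unadjusted t test. A Mann-Whitney test on the same data (5,000 runs) gives 73.8%.

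**Type I error.** In simulation it is 0.050 for the unadjusted t test, 0.049 with arm in the model, and 0.042 for Mann-Whitney. There is no inflation.

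**Chance imbalance.** If the share of STAND men differed by 15 percentage points between marker groups (assumption), the shift would be 12 × 0.15 = 1.8 points. The standard error with 32 per group is 18.03 × √(2/32) = 4.5 points, so the shift is 0.4 standard errors. The unadjusted standard error already allows for imbalance of this kind.

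**Limits.** The 12-point effect is given for body fat only. The documents give no arm effect for glucose, insulin, body mass index, waist, quality of life or HR-pQCT, so the loss there cannot be sized. The Mann-Whitney figure is an illustration on the body-fat scale, not an estimate for quality of life.

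**The case against.** The strongest reply is that the planned SNP and 2D:4D tests are valid. Both traits are set before randomisation, so arm cannot confound them systematically, and chance imbalance is inside the standard error. That stands. The SNP extension to further risk factors could also include arm and drugs; they are unnamed, not ruled out. The 2D:4D test has no such extension. The full loss needs the full 12-point effect and nearly disappears at half of it. The SNP work is called exploratory (Section 1.3.5.1), and both genotyping and HR-pQCT are optional.

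A reader might infer more than the documents support:

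- *That arm is absent from all correlative analyses.* It is not: an HR-pQCT comparison between arms is planned.
- *That the pooled HR-pQCT mean fails because it is not change on ADT alone.* The endpoint in Section 9.7.3 is change after 12 months of ADT, and nothing says without supportive care. Usual care would not supply that quantity either. Those men may use exercise, nutrition and symptom services (Section 3.1), and Section 7.8 allows added bone drugs in either arm. How far the pooled mean differs from the usual-care mean cannot be calculated from the documents.
- *That added drugs are ignored.* All five SNP outcomes are primary or secondary endpoints with a starter rule in Section 9.8.1 or 9.8.2. Section 9.8.3 is silent on whether those rules carry over; only HR-pQCT clearly lacks one.
- *That the chemohormonal men are pooled into HR-pQCT.* The wording on the study population is ambiguous, and that cohort's stated objectives do not mention HR-pQCT.

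**Conclusion.** The point holds as a modest loss of precision, with no bias and no type I error inflation. The main SNP tests and the 2D:4D test leave out a known source of variance that the trial itself expects to matter. On the Section 9.2 figures for body fat, and assuming 64 evaluable men with marker data and a common SD of 17, the SD rises by 6.0%, 64 men count as about 57, and 80% power becomes about 75%. If fewer men consent to genotyping, the relative loss is about the same. With an arm effect of 6 points or less, the SD rises by at most 1.5%. For HR-pQCT, drug starters and the chemohormonal cohort, what is missing is clear wording and a by-arm summary; no error in a planned test is shown. Severity is low.

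**What to change.** In Section 9.8.3:

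1. Include randomised arm as a fixed covariate in every SNP model. For dominant or recessive coding, replace the two-group test with a linear model containing genotype and arm.
2. Test 2D:4D group against change in quality of life and change in empathy by an arm-stratified rank test (van Elteren) or an arm-adjusted model. The baseline empathy comparison does not need arm.
3. For HR-pQCT, report mean change for each arm beside the pooled mean and keep the planned between-arm test. Show any chemohormonal patients separately.
4. Apply the Section 9.8.2 approach to HR-pQCT, with results with and without men who start bone agents. State whether the starter rules in Sections 9.8.1 and 9.8.2 carry over to the SNP and 2D:4D analyses.

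The cost is SAP wording, one degree of freedom per model and smaller groups in the HR-pQCT description. Randomised arm and concomitant medication are already recorded, so no new data are needed.

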1.3.5.3 Second Digit: Fourth Digit Length Ratio and Fetal Testosterone Exposure

The ratio between the length of the 2nd and 4th digits, typically measured on the right hand, is a physical trait that correlates with fetal testosterone exposure. The finding can be measured throughout life and correlates with physical manifestations and disease processes that are associated with androgen excesses such as autism, myocardial infarction and prostate cancer. It has also been associated with behavioral traits that are commonly associated with androgen excess, such as risk taking.

Although the link between 2d:4d ratio and prostate cancer has been established in one study patient with a positive 2d:4d ratio (index finger longer than the ring finger on the right hand) had a 33% reduced risk of prostate cancer.

Given that it is a marker of brain 'priming' by testosterone, we hypothesize that patients with a higher 2d:4d ratio (greater testosterone exposure in utero) will be more sensitive to changes in serum testosterone at any point in life and therefore will experience a greater degree of typical androgen deprivation toxicities (hot flushes, decreased quality of life, mood swings etc.) than those with a lower ratio.

The ratio is measured on the right hand and can be performed at any point in study entry.

2. Hypothesis and Study Objectives

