3.2.3 Correlative Study Endpoints

- Association between inherited genetic polymorphisms of functional relevance near or within genes encoding proteins with roles in steroid hormone transport and androgen receptor signaling with changes in metabolic parameters among men treated with androgen deprivation therapy.
- Mean change from baseline in trabecular bone architecture as measured by trabecular bone number (TbN) and trabecular bone volume fraction (BV/TV) after 12 months of androgen deprivation therapy.
- Association between 2D:4D ratio with change in quality of life on androgen deprivation therapy.
- Association between 2D:4D ratio with baseline empathy score as measured by validated questionnaire.

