7.2 Screening Visit (within 6 weeks of Day 1 of Study)

Screening procedures and informed consent as well as written health information authorization must be completed within 6 weeks of day 1 of study. All research-related procedures will be conducted after patient has signed written consent to participate in the study.

These procedures include:

- Physical exam and medical history
- Demographics and disease characteristics:
 - Date of prostate cancer diagnosis
 - Gleason grade and PSA at the time of diagnosis
 - Type and date of prior local therapy (if any)
 - Date of ADT initiation and indication (adjuvant, biochemical relapse, or metastatic disease)
 - Concurrent use of anti-androgen (yes/no)
 - Concurrent radiation therapy (yes/no)
 - Metastatic status at time of study entry (none, bone only, soft tissue, any visceral)

Clinical Assessment

- Co-morbidity assessment by Charlson Co-morbidity Scale (Appendix 3)
- Quality of life questionnaires (see Appendix 2):
 - SF-12, EPIC-26, HFRDIS, Lee Fatigue Scale, PHQ-9, Attentional Functional Index, exercise patterns, empathy scale
- Concomitant medication
- Weight and body mass index
- Assessment of ratio of 2nd digit to 4th digit finger length using caliper assessment

Radiographic Assessment

- DXA Bone Density Scan (completed within 12 weeks of Day 1 of study)
- High resolution peripheral quantitative CT scan of the distal tibia and radius (optional)

Laboratory Assessment

- Baseline PSA measurement
- Serum testosterone (if prior receipt of androgen deprivation therapy)

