9.4 Accrual

A total of 80 patients will be enrolled in the randomized patient cohort at the University of California San Francisco. Study accrual is anticipated to be approximately 2 patients per month, leading to total study accrual duration of 40 months. Anticipated time from last patient enrolled to primary study completion and analysis of primary and secondary endpoints equals approximately 12 months, leading to an estimated primary study duration of 52 months. A total of 20 patients will be enrolled in the non-randomized chemohormonal cohort, at an estimated frequency of 0.8 patients/month, leading to an estimated accrual period of 24 months.

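### The continuous 2D:4D ratio is tested only after a median split, which costs about a third of the information that Spearman correlation would keep; a minor point in a correlative analysis

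*Combined protocol and SAP*

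**What the plan says.** Section 9.8.3 first states that "The distribution of the 2D:4D finger length ratio will be determined for the entire study population". It then gives a reason for grouping, "As the optimal cut-off to define sensitivity to androgen deprivation therapy is not known", and the consequence: "the study cohort will be dichotomized into those with 2D:4D ratios above and below the median respectively". The outcomes, percent change in questionnaire scores and both baseline and percent change in empathy score, "will be compared between dichotomized subgroups using the Mann-Whitney test".

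The endpoint in section 3.2.3 is worded as an association: "Association between 2D:4D ratio with change in quality of life on androgen deprivation therapy". Section 9.7.3 does the same, and section 2.2.3 speaks of a relationship. The measurement is described in section 7.2 as "Assessment of ratio of 2nd digit to 4th digit finger length using caliper assessment". The hypothesis in section 1.3.5.3 is that men with a higher ratio "will be more sensitive to changes in serum testosterone at any point in life" and so have more toxicity than men with a lower one; it names no cut-point. None of these sections gives a correlation, a regression or any other analysis that uses the ratio as measured.

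**The concern.** The stated reason argues against the choice. If no cut-off is known, the natural course is not to cut. A median split treats two men just either side of the median as different and all men within a half as alike, and the cut value depends on who happens to enrol.

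The same section handles another predictor without this loss: under the additive model, SNP genotype enters a generalized linear model as a graded 0, 1, 2 score.

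What is at stake is power. These comparisons have no sample-size justification, the cohort is small, and section 9.8 sets significance at 0.05. A null result from the split would say less about the hypothesis than the same data could.

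**Working it through.** **The plan's own figure.** There is none for 2D:4D. The only power statement for the randomized cohort (section 9.2) concerns body fat, and it reproduces: 2 × (1.96 + 0.8416)² / 0.71² = 31.1, so 32 per arm; exact t-test power at 32 per arm is 79.8%; 32 / (1 − 0.20) = 40 per arm.

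**Inputs.** Section 9.4: "A total of 80 patients will be enrolled in the randomized patient cohort", plus 20 in the chemohormonal cohort. Section 9.8.3 refers to the entire study population, so n could be 80, or 100 with the pilot cohort. I take 64 as a low case by borrowing the 20% inevaluable rate of the body-fat endpoint: 80 × 0.8 = 64. That is an assumption, and the baseline empathy comparison needs no month-12 data at all. The correlation r is also an assumption; I show 0.1 to 0.3. Tests are two-sided at 0.05.

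**Efficiency.** Mann-Whitney and Spearman both use the ranks of the outcome, so the outcome side cancels. What differs is how the ratio X enters: as a two-group indicator or as ranks. For a linear relation, the efficiency of each form relative to X itself is its squared correlation with X.

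- Normal X, median split: 2/π = 0.637
- Normal X, ranks: 3/π = 0.955
- Planned split against Spearman: 0.637 / 0.955 = 0.667, a 33% loss

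On this scale 64, 80 and 100 men act like 64 × 2/3 = 43, 80 × 2/3 = 53 and 100 × 2/3 = 67.

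**Other distributions of the ratio.** Against linear use of X, the loss from splitting is 25% if X is uniform (efficiency 0.75), 36% if normal (0.637) and 50% if double exponential (0.50). Against Spearman it is 25% for uniform X, since ranks lose nothing there. For double-exponential X the ranks have efficiency 27/32 = 0.844, so the ratio is 0.50 / 0.844 = 0.593, a 41% loss.

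**Power by simulation** (bivariate normal; 20,000 runs per setting for r = 0, 0.2 and 0.3; separate runs differ by a point or so):

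| Assumed r | n = 64: Spearman / split | n = 100: Spearman / split |
|---|---|---|
| 0 | 5% / 5% | 5% / 5% |
| 0.1 | 11% / 9% | 15% / 12% |
| 0.2 | 32% / 23% | 48% / 34% |
| 0.3 | 63% / 46% | 82% / 65% |

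At n = 80 and r = 0.3 the figures are 74% and 55%. With n = 64 and r = 0.3 they are 67% and 53% for a uniform ratio, and 57% and 38% for a double-exponential one.

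**The case against.** The strongest reply is that this is one correlative analysis among several. It has no power claim and no multiplicity adjustment, and it has no bearing on the primary or secondary endpoints or on any interim decision. Fixing the cut at the median in advance also avoids a search for a favourable cut-off, and it keeps type I error at about 5%. All of that stands, and it limits the severity.

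Section 9.8.3 does contemplate a cut-off that marks sensitivity to therapy. If a true step lay at the median, the split would be the better test: the squared correlation of ranks with a median indicator is (1/4)² / (1/12) = 0.75, so Spearman would lose up to a quarter. The documents posit no such step. Section 1.3.5.3 does mention an index finger longer than the ring finger, but in connection with the risk of prostate cancer, and that is not the sample median.

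A reader might infer several stronger things that the documents do not support:

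- That power is lower for every 2D:4D comparison. This fails if there is a step near the median, and at r = 0.1 the difference is only 2 to 3 points.
- That the result cannot be compared with other cohorts. The distribution of the ratio is to be determined, so the cut value can be reported.
- That a linear model would gain still more. At n = 64 and r = 0.3, Pearson correlation reaches 68% with normal data. Percent changes in scores with a floor at zero, such as PHQ-9 and HFRDIS, are likely to be skewed. With a log-normal outcome Pearson falls to about 51%, while Spearman (62%) and the split (45%) are essentially unchanged. Only the Spearman advantage is robust to this.

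**Conclusion.** The point holds as a minor one. The planned split is valid but inefficient for the stated objective. The loss against Spearman is about one third if the ratio is roughly normal and the relation is monotone and near-linear. It is about 25% if the ratio is uniform. If it is double exponential the loss is about 41% against Spearman and 50% against linear use of the ratio. In power, this is about 17 to 19 points at r = 0.3 over n = 64 to 100, about 9 to 14 at r = 0.2, and little at r = 0.1, where neither test has useful power. The values of n and r are assumptions, because the documents supply neither for this analysis. False-positive risk is not affected.

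**What to change.** In section 9.8.3, state that the main 2D:4D analysis is the Spearman correlation of the continuous ratio with the outcomes already named (percent change in each quality-of-life score; baseline and percent change in empathy score), reported with confidence intervals. Keep the median split for tables and plots only, and report the cut value.

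Regressing the month-12 score on the ratio with adjustment for baseline and arm is a different proposal. It would replace the percent-change outcome and add assumptions for bounded scores, so it is not needed to remove the split. Spearman does not adjust for arm, but neither does the planned test.

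The cost is a wording amendment, which under section 10.4 needs PRC and CHR approval, and some loss of power if there is in truth a step near the median. No new data, visits or patients are required.
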